5.8. Reporting Pregnancy

During study participation, all subjects should be instructed to contact the investigator immediately if they suspect they might be pregnant (e.g., missed or late menstrual period). If pregnancy is confirmed, Investigational Product must be discontinued immediately, the subject should be referred to an obstetrician experienced in reproductive toxicity for evaluation and counseling, and the subject should be followed until conclusion of the pregnancy.

The investigator is responsible for reporting all available pregnancy information on the pregnancy report and submitting to the Medical Monitor within 24 hours of becoming aware of the event, although pregnancy itself is not considered an AE. Follow-up information detailing the outcome of the pregnancy and the health of the newborn should be reported as it becomes available. Any pregnancy complication must be reported as a SAE. In addition, any pregnancy resulting in a congenital abnormality or birth defect of the newborn, or neonatal death occurring within 30 days of the birth must be reported as a SAE, regardless of causality. Any infant death that occurs after the 30 day reporting period that the investigator suspects is related to Investigational Product must also be reported as an SAE.

Partner pregnancies of a male subject do not need to be reported.

5.9. Treatment Stopping Rules

If a subject has non-cutaneous adverse events of concern, clinically significant laboratory values or any condition that the investigator determines could possibly be related to the study drug, the Investigator should immediately contact the Medical Monitor to discuss if the subject should be discontinued from treatment with investigational product.

Treatment for any individual subject will be discontinued if the subject experiences:

- A serious adverse event (SAE) or a clinically significant non-serious AE which in the opinion of the Principal Investigator or Medical Monitor warrants discontinuation from the study for that subject's well-being.
- A treatment-emergent severe (Grade 3) laboratory abnormality (confirmed by repeat sample; see Appendix 13 for more information).

A subject with a PHQ-8 or modified PHQ-A score ≥ 15 should receive immediate referral to a mental health professional, and Investigators in consultation with the mental health professional should consider interruption or discontinuation of the study drug.

• Subjects with a PHQ-8 or modified PHQ-A score of 10-14 should be referred to a mental health professional for evaluation, regardless of the reason for their change in score

Subjects with a CDI-2 raw total score of \geq 32 should be referred to a mental health professional, and Investigators in consultation with the mental health professional should consider interruption or discontinuation of the study drug

• Subjects with a CDI-2 raw score of ≥21 for females and ≥22 for males should be referred to a mental health professional for evaluation

A subject that is experiencing suicidal ideation and behavior should be referred immediately to a qualified mental health care provider and consideration given to discontinuation from study drug.

As noted above, study treatment must be discontinued immediately in the event of a female subject's pregnancy.

Treatment should be interrupted:

• If a subject develops an application site reaction with the clinical appearance of an 'irritation reaction', and with a severity of a Dermal Response Score of 5 (erythema, edema and papules) or greater on the scale of Berger and Bowman, treatment should be interrupted for up to one week and may then be resumed if the reaction has, in the opinion of the Investigator, adequately resolved.

Treatment should be discontinued:

• If the application site reaction reoccurs, treatment should be discontinued permanently, and the subject followed until the reaction resolves.

For cases of suspected allergic contact dermatitis, the medical monitor and sponsor should be notified and there should be discussion about performing patch testing to further evaluate. Patch testing is encouraged in such cases.

In the event of a medical emergency where unblinding is required to provide medical care to the subject, refer to the most current IWRS User Manual (Section 4.8.3). Contact the Medical Monitor and the Sponsor promptly.

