	24. Parent(s)/legal guardian(s) who are unable to communicate, read, or understand the local language(s). Subjects who are unable to communicate, read or understand the local language, or who display another condition, which in the Investigator's opinion, makes them unsuitable for clinical study participation.
	25. Subjects who are family members of the clinical study site, clinical study staff, or sponsor, or family members of enrolled subjects living in the same house.
Key Assessments:	Safety Assessments
	• Safety will be monitored through local tolerability assessments, vital signs, physical examination, safety labs, Children's Depression Inventory 2 (CDI-2, parent report for children 6-11 years old, inclusive), modified PHQ-A (for adolescents 12-17 years old, inclusive), PHQ-8 (for adults), C-SSRS (for adolescents and adults 12 years old and older), and AEs.

	• After obtaining consent, all AEs and TEAEs should be collected.					
	• The investigator or a properly trained and designated subinvestigator will perform local tolerability assessments at Baseline/Day 1, and Weeks 1, 2, and 4 (Days 8, 15, and 29). Subjects will have vital signs measured at each study visit. Height will be collected at Visit 1 (Screening) only.					
	 A limited physical exam (skin, lungs, and heart only) will be performed at Screening, Baseline/Day 1 and Week 4/Day 29. Blood and urine samples for routine safety laboratory tests (hematology, serum chemistry, and urinalysis) will be obtained at Screening, Baseline/Day 1 and Week 4/Day 29. For all female subjects of childbearing potential, a urine pregnancy test will be administered at all clinic visits except for Screening where a serum pregnancy test will be performed. A negative pregnancy result is required for continued participation in the study, and results (of the urine pregnancy test) must be available prior to dispensing of study drug at study visits. 					
	Efficacy Assessments					
	• Efficacy assessments will include vIGA-AD (Appendix 7), EASI, WI-NRS, BSA, DLQI/CDLQI (Appendix 8 and Appendix 9), DFI (Appendix 10), SCORAD (Appendix 11), and POEM (Appendix 12).					
	Pharmacokinetic Assessment					
	• A single PK assessment (trough) will be performed in all subjects with a blood sample collected at Week 4/Day 29.					
Study Endpoints:	 The Primary Efficacy Endpoint will be tested in all randomized subjects and defined as: 					

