5.6. Unscheduled Visit

Unscheduled visits may be necessary to repeat testing following abnormal laboratory results, for follow-up of AEs, or for any other reason, as warranted in the judgement of the Investigator.

The following information will be collected for all subjects:

- Concomitant medications/procedures
- AEs

The following information also will be collected:

- vIGA-AD and EASI
- BSA affected with AD

• Local tolerability assessment (by Investigator)

The rules for how to tally vIGA-AD, BSA or other proportions of categorical responses will be described in the Statistical Analysis Plan.

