6.10. Local Tolerance Assessment

For Investigator's assessment, the numeric application site reaction scores will be summarized individually by using number and percentage of subjects by visit, as well as mean/median scores.

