5.4 Windowing Conventions

Visits will be analysed as scheduled. Unscheduled, early termination visits, and/or retest measurements will only be included if a scheduled measurement is not available and the early termination or unscheduled/retest measurement falls within the analysis visit windows as described in Table 2, Table 3, and Table 4 when appropriate. Unscheduled/retest measurements will be listed.

If there is more than one assessment for a given timepoint and analysis visit when a scheduled measurement is not available, the assessment closest to the target day will be considered.

Table 2 Analysis Visit Windows for Efficacy Endpoints, Vital Signs, CDI-2, PHQ-8, PHQ-A, C-SSRS and Local Tolerability Assessment

Analysis Visit	Target Day	Lower Limit	Upper Limit
Week 1	8	2	11
Week 2	15	12	22
Week 4	29	23	43

	STATISTICAL ANALYSIS PLAN, Version 1.0
Protocol Number: ARQ-151-312	Sponsor: Arcutis Biotherapeutics, Inc.

Table 3 Analysis Visit Windows for Clinical Laboratory, Physical Examination and PK assessment

Analysis Visit	Target Day	Lower Limit	Upper Limit
Week 4	29	23	43

Table 4 Windows for the derivation of Average Weekly WI-NRS

Days for calculation of weekly average	Week (Derived)
(-7, -1)*	Baseline
(1, 7)	Week 1
(8, 14)	Week 2
(15, 21)	Week 3
(22, 28)	Week 4

^{*} Day 1 WI-NRS score will be used to calculate the value for week 1 only when it is collected after the application of the first first study drug. If Day 1 WI-NRS score is collected prior to or concurrently with the application of the first study drug, then the Day 1 WI-NRS score will be included in baseline calculation.

Note: With the following caveat, if more than one WI-NRS score is available on the same day, the worst score of the day will be considered in the analyses. The caveat is that if a subject has two WI-NRS assessments on Day 1 and one of them was collected before the first study treatment dosing while the other one was collected after the first study drug dosing. Under such circumstances, the assessment collected before the first study drug dosing will be considered for the Baseline analysis visit while the assessment collected after the first study drug dosing will be considered for the Week 1 analysis visit.

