13.4 Local Tolerability Assessments

The investigator's assessment of the application site reaction will be summarized by visit using both categorical methods (number and percentage of subject with each score) as well as continuous methods (e.g., mean, standard deviation, etc.)

Local tolerability (burning/stinging sensation) assessed by the subject will be summarized using number and percentage similarly.

	STATISTICAL ANALYSIS PLAN, Version 1.0
Protocol Number: ARQ-151-312	Sponsor: Arcutis Biotherapeutics, Inc.

13.5 Patient Health Questionnaire Depression Scale (PHQ-8) and Patient Health Questionnaire Depression Scale (Modified PHQ-A)

The Modified PHQ-A Assessment will be performed in adolescent subjects (12-17 years old, inclusive; question 9 has been removed since that is better evaluated by use of the C-SSRS tool).

The PHQ-8/Modified PHQ-A score is the sum of the responses for the questions, each question ranging from 0 (Not at all) to 3 – (Nearly every day). Five severity categories of depression are defined as follows:

- None Minimal depression (0 to 4)
- Mild depression (5 to 9)
- Moderate depression (10 to 14)
- Moderately severe depression (15 to 19)
- Severe depression (20 to 24)

The score will be set to missing in case of at least one missing value. The number and percentage of subjects in each category will be summarized by treatment and visit. A summary of the shifts in depression category from baseline to each study visit will also be provided.

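### A Dermal Response score of 5 or more recorded at an unscheduled visit can be missing from every by-arm tolerability summary, because the by-visit table prefers the scheduled score and no worst post-baseline score is planned

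*Protocol*

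**What the plan says.** **Trigger.** Protocol 5.9 sets interruption for an irritation reaction "with a severity of a Dermal Response Score of 5 (erythema, edema and papules) or greater on the scale of Berger and Bowman". In that event "treatment should be interrupted for up to one week and may then be resumed", provided the investigator judges the reaction adequately resolved. The section does not say at what kind of visit the reaction is found.

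**When scores are taken.** The investigator scores tolerability at Baseline and on Days 8, 15 and 29, each post-baseline visit with a window of 3 days either side (Protocol 1.1 and the visit schedule). Protocol 5.6 allows unscheduled visits "for follow-up of AEs, or for any other reason, as warranted in the judgement of the Investigator", and lists the investigator's local tolerability assessment among the items to collect there.

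**What is tabulated.** Protocol 6.10 has the scores "summarized individually by using number and percentage of subjects by visit, as well as mean/median scores". SAP 13.4 agrees: "The investigator's assessment of the application site reaction will be summarized by visit", with category counts and continuous statistics. Neither mentions a worst post-baseline score or a count at or above 5.

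**Which record is used.** SAP 5.4 states that unscheduled, retest and early-termination measurements "will only be included if a scheduled measurement is not available" and they fall inside the analysis window. Table 2 of that section covers Local Tolerability: Week 1 is Days 2 to 11, Week 2 is Days 12 to 22, Week 4 is Days 23 to 43. If the scheduled value is missing and several others qualify, the one nearest the target day is taken. SAP 5.8 refers back to these rules and says all such data will be listed.

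**The concern.** The protocol names its own level of irritation that matters, and the score at that level is collected when a subject comes in between visits. The record-selection rule then sets that score aside in favour of the scheduled one. If the reaction has fallen below 5 by the next scheduled visit, the by-visit table shows only lower scores for that subject.

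Local tolerability is a named safety endpoint (SAP section 2), and Protocol 2.4 gives good local toleration as part of the case for developing the cream. A reader of the planned table could see no score of 5 or more in an arm where such scores were recorded, and the table would give no sign of it.

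**Working it through.** The documents state no figure on this point, so there is none to reproduce. The check has two parts.

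**1. Following one record through the rules (hypothetical subject).** Scheduled scores: 1 on Day 15 and 0 on Day 29. Unscheduled score: 6 on Day 20.
- Day 20 lies in the Week 2 window (Days 12 to 22).
- The scheduled Day 15 score exists, so SAP 5.4 excludes the Day 20 score from Week 2.
- Week 4 takes the Day 29 score.
- The table shows 1 and 0. The 6 is listed only.

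The displacing score is not always the later one. Unscheduled scores on Days 9 to 11 (3 days) and Days 16 to 22 (7 days) fall in the window of the visit already held, so 3 + 7 = 10 of the 25 non-visit days between Day 2 and Day 28 are displaced by a score taken before the reaction. In either case the reaction reaches the table only if it is still at 5 or more at the next scheduled visit.

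**2. How loss depends on duration (illustration).** Assumptions, none from the documents: the score reaches 5 on a start day spread evenly over Days 2 to 29 (28 days) and stays there for L consecutive days; all scheduled visits are attended on Days 8, 15 and 29. The gaps are 7, 7 and 14 days. In a gap of g days, the start days whose reaction covers no scheduled score number max(0, g − L).

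Missed = 2 × max(0, 7 − L) + max(0, 14 − L), out of 28.

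| L (days) | to Day 8 | Day 8 to 15 | Day 15 to 29 | Missed |
|---|---|---|---|---|
| 1 | 6/7 | 6/7 | 13/14 | 25/28 = 89% |
| 3 | 4/7 | 4/7 | 11/14 | 19/28 = 68% |
| 5 | 2/7 | 2/7 | 9/14 | 13/28 = 46% |
| 7 | 0/7 | 0/7 | 7/14 | 7/28 = 25% |
| 10 | 0/7 | 0/7 | 4/14 | 4/28 = 14% |
| 14 | 0/7 | 0/7 | 0/14 | 0/28 = 0% |

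From 7 days upward, every missed start day lies between Day 15 and Day 29. The visit windows move these counts: the last gap can run from 26 − 18 = 8 days to 32 − 12 = 20 days.

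These shares concern reactions that scheduled scoring would not catch. A recorded score is lost only if the subject also attends an unscheduled visit while the score is 5 or more. With the scheduled visits attended, each window has a scheduled score and the unscheduled one is always displaced.

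**With the fix.** A worst-score summary over all assessments would tabulate every recorded score of 5 or more, so none recorded would be lost.

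**The case against.** The strongest reply is that the loss is contingent and partly covered elsewhere.

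- Protocol 5.9 names no visit type. A reaction present on Day 8, 15 or 29 is tabulated in full, and one that has not resolved will still be there at the next scheduled score. **This stands**, and it limits the point to between-visit reactions that have subsided.
- Unscheduled scores are used when the scheduled one is missing. **This stands**, although the rule then picks the nearest score and not the worst.
- SAP 13.1 tabulates application-site TEAEs by SOC and PT, and all TEAEs by maximum severity. **This stands in part.** Severity there is the CTCAE grade (Protocol 5.7.5), so the count at the Dermal Response threshold cannot be recovered. The adverse event overview counts discontinuations but not interruptions, and SAP 11 counts subjects missing more than 3 consecutive doses without the reason.
- All unscheduled data are listed. True, but a listing gives no by-arm count.
- SAP 13 plans no inferential safety test, so no formal comparison changes. **This stands.**

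Two stronger readings are tempting. A reader might infer that most such scores are lost because the next scheduled visit often falls while cream is withheld: of 25 non-visit onset days, 18 (72%) for a 7-day hold, 12 (48%) for 5 days and 6 (24%) for 3 days. Those counts are arithmetically right but measure visits off cream, not scores lost. Resumption depends on resolution, so a visit during the hold may well be one at which the reaction is still visible. The counts also rise with the length of the hold, whereas missed reactions fall as the reaction lasts longer. A reader might also infer that a difference between roflumilast and vehicle is shrunk. The documents give no rate of scores of 5 or more in either arm, so that cannot be said.

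**Conclusion.** The point holds as a gap in a descriptive safety summary. The by-visit rule can leave a recorded Dermal Response of 5 or more out of every by-arm tolerability summary, and no planned table restores it. The documents do not support saying that the worst reactions **are** absent, that withholding cream ensures they subside before the next score, or that interrupting reactions are found at unscheduled visits. They support only that such scores **can** be absent.

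The size is unknown. The duration table shows direction only: short reactions are the ones at risk, mainly after Day 15. The primary and secondary efficacy analyses are unaffected.

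One limit: Protocol 5.6 and 5.9 were read in the original version, while the SAP follows Amendment 3, so the amended wording of those sections could not be checked. The record-selection and tabulation rules are those of the SAP supplied.

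**What to change.** In SAP 13.4:

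1. Add a table, by arm in the safety population, of each subject's worst post-baseline Dermal Response over all scheduled, unscheduled and early-termination assessments, with the number and percentage of subjects reaching 5 or more.
2. State that the selection rule in SAP 5.4 does not apply to this table.
3. Keep the by-visit table, with a footnote identifying scores taken while treatment was interrupted.

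The cost is one extra descriptive table from scores already collected. The tolerability figures may look slightly less favourable. The plan already takes the worst value elsewhere: maximum TEAE severity in SAP 13.1, and laboratory shifts to the worst post-baseline grade in Protocol 6.6. Nothing in the interruption rule or in clinical management needs to change for this.

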6. DATA ANALYSIS

Data will be handled and processed according to the Contract Research Organization's Standard Operating Procedures, which are written based on the principles of GCP.

6.1. Statistical Methods

The methodology presented below is a summary of the more detailed analysis plan that will be presented in the Statistical Analysis Plan (SAP). The SAP will be finalized before the database is locked and unblinded. Any changes to the methods described in the final SAP will be described and justified in the clinical study report.

All statistical processing will be performed using SAS® (Version 9.4) unless otherwise stated.

6.2. Determination of Sample Size

There are approximately 650 subjects planned for this study. In order to test the key secondary endpoint of IGA success in subjects with a vIGA-AD score of 'Moderate' at randomization, approximately 488 of the subjects to be accrued will have vIGA-AD score of 'Moderate' at randomization. Randomization will be stratified by vIGA-AD score ('Mild' vs. 'Moderate') and by study site.

This sample size provides approximately 95% power to detect an overall 15% difference between treatment groups on vIGA-AD success at Week 4 at α -0.05 using a 2-sided stratified (vIGA-AD at randomization and study site) Cochran-Mantel-Haenszel test. The results from a recent phase 2 study (ARQ-151-212) of ARQ-151 cream 0.15% compared to vehicle treatment were used to estimate the treatment difference. Specifically, in the phase 2 trial, approximately 37% of subjects demonstrated vIGA-AD success at Week 4 in the ARQ-151 0.15% group compared to 22% in the vehicle group. This sample size also provides approximately 90% power to detect an overall 17% difference between treatment groups on IGA success at Week 4 among subjects with vIGA-AD score 'moderate' at randomization. The same testing method, the stratified Cochran-Mantel-Haenszel test, will be used as for the primary endpoint.

To control for multiple comparisons, the key secondary endpoint will only be tested if the primary endpoint demonstrates statistical significance. In addition, the remaining secondary endpoints will be inferentially tested only if the primary and key secondary endpoint comparisons are statistically significant. To control for multiple comparisons among the remaining secondary endpoints, partitioning of alpha and the Holm's procedure will be used.

6.3. Subjects to Analyze

The analysis populations are defined as follows:

- Safety population will include all subjects who are enrolled and received at least one confirmed dose of study medication.
- Intent-to-Treat (ITT) population will include all subjects who are randomized.
- vIGA-AD Moderate ITT population will be a subset of the ITT population with vIGA-AD score 'moderate' at randomization.
- WI-NRS population will be a subset of the ITT population with WI-NRS score \geq 4 at baseline.
- Pharmacokinetic (PK) population will include all subjects receiving the active drug with quantifiable plasma concentrations of roflumilast.

6.4. Background and Demographic Characteristics

Descriptive statistics will be used to summarize demographic characteristics (age, sex, ethnicity, and race) and background characteristics for the randomized subjects.

6.5. Study Medication Compliance

The number of study drug applications by each subject based on diary data will be summarized using summary statistics (mean, standard deviation [SD], median, minimum, and maximum), and categorically.

The number of investigational product applications by each subject based on diary data will be summarized using descriptive statistics.

The amount of investigational product used by each subject based on tube weight will be summarized by treatment using descriptive statistics, and categorically.

Investigational product application compliance will be calculated based on number of applications divided by the expected number (amount) of investigational product applications for each subject. Compliance will be summarized descriptively by treatment group.

